5.3.3. Activity

- Participants will abstain from strenuous exercise from the time of their check-in activity and throughout the stay at clinical facility. Participants may participate in light recreational activities during studies (e.g., watching television, reading).
- Participants will be advised to avoid exposure to intense natural or artificial sunlight until completion of 5 days post last dose.

5.4. Screen Failures

Screen failures are defined as participants who consent to participate in the clinical study but are not subsequently randomized in the study. A minimal set of screen failure information is required to ensure transparent reporting of screen failure participants to meet the Consolidated Standards of Reporting Trials (CONSORT) publishing requirements and to respond to queries from regulatory authorities. Minimal information includes demography, screen failure details, eligibility criteria, any protocol deviations and any serious adverse events (SAEs).

Individuals who do not meet the criteria for participation in this study (screen failure) may not be rescreened.

6. STUDY TREATMENT

Study treatment is defined as any investigational intervention(s), marketed product(s), placebo, or medical device(s) intended to be administered to a study participant according to the study protocol.

6.1. Study treatment (s) Administered

Treatment Code	T1	T2	R
Treatment Name	Griseofulvin Tablets, 500 mg	Griseofulvin Tablets, 250 mg	Griseofulvin Tablets, 500 mg (Grisovin Aspen Pharma Pty Ltd, Australia)
Type	Test Drug	Test Drug	Reference Drug
Dose Formulation	tablet	tablet	tablet
Unit Dose Strength(s)	500 mg	250 mg	500 mg
Dosage Level(s)	1 tablet	1 tablet	1 tablet
Route of Administration	oral	oral	oral
Use	experimental	experimental	active-comparator
IMP and NIMP	IMP	IMP	IMP
Sourcing	Provided by the Sponsor	Provided by the Sponsor	Provided by the Sponsor
Packaging and Labeling	Study treatment will be provided in container. Each container will be labeled as required per country requirement.	Study treatment will be provided in container. Each container will be labeled as required per country requirement.	Study treatment will be provided in container. Each container will be labeled as required per country requirement.

6.2. Preparation/Handling/Storage/Accountability

1. The investigator or designee must confirm appropriate temperature conditions have been maintained during transit for all study treatment received and any discrepancies are reported and resolved before use of the study treatment.
2. Only participants enrolled in the study may receive study treatment and only authorized site staff may supply or administer study treatment. All study treatments must be stored in a secure, environmentally controlled, and monitored (manual or automated) area in accordance with the labeled storage conditions with access limited to the investigator and authorized site staff.
3. The investigator, institution, or the head of the medical institution (where applicable) is responsible for study treatment accountability, reconciliation, and record maintenance (i.e., receipt, reconciliation, and final disposition records).
4. Further guidance and information for the final disposition of unused study treatment are provided in the CRO's Standard Operating Procedure.
 - Under normal conditions of handling and administration, study treatment is not expected to pose significant safety risks to site staff.
 - A Material Safety Data Sheet (MSDS)/equivalent document describing occupational hazards and recommended handling precautions either will be provided to the investigator, where this is required by local laws, or is available upon request from GSK.

6.3. Measures to Minimize Bias: Randomization and Blinding

This is an open-label study; potential bias will be reduced by the following steps: The randomization for this study will be generated by PBS personnel using the PROC PLAN on statistical software SAS[®] 9.2 or a higher version at CRO. The handling of randomization will be done as per the CRO's Standard Operating Procedure.

The analyst from bioanalytical facility will be blinded to the sequence of administration of Test and Reference product to the individual participant.

6.4. Study treatment Compliance

- When participants are dosed at the site, they will receive study treatment directly from the investigator or designee, under medical supervision. The date and time of each dose administered in the clinic will be recorded in the source documents. The dose of study treatment and study participant identification will be confirmed at the time of dosing by a member of the study site staff other than the person administering the study treatment. Study site personnel will examine each participant's mouth to ensure that the study treatment was ingested.
- Record of dosing for individual participant will be maintained in the CRF.

6.5. Concomitant Therapy

Any medication or vaccine (including over-the-counter or prescription medicines, vitamins, minerals and/or herbal supplements) that the participant is receiving at the time of enrolment or receives during the study must be recorded along with:

- reason for use
- dates of administration including start and end dates
- dosage information including dose and frequency

The Medical Monitor should be contacted if there are any questions regarding concomitant or prior therapy.

Participants must abstain from taking prescription or non-prescription drugs (including vitamins and dietary or herbal supplements) within 14 days before the start of study treatment until completion of the follow-up visit, unless, in the opinion of the investigator and sponsor, the medication will not interfere with the study.

In case of any illness requiring unacceptable medication, Paracetamol/Acetaminophen/Diclofenac is permitted for use any time during the study as per discretion of investigator in consultation with the Medical Monitor. Other concomitant medication may be considered on a case-by-case basis by the investigator in consultation with the Medical Monitor if required.

6.6. Dose Modification

Refer to Section 4.3 for selection of each participant's dose of study.

6.7. Treatment after the End of the Study

As this is the single dose bioequivalence study to be conducted in healthy participants, no treatment at the end of study will be provided.

7. DISCONTINUATION OF STUDY TREATMENT AND PARTICIPANT DISCONTINUATION/WITHDRAWAL

7.1. Discontinuation of Study Treatment

It may be necessary for a participant to permanently discontinue (definitive discontinuation) study treatment in subsequent study period only if the participant is withdrawn from the study due to any adverse event, serious adverse event or non-compliance to the protocol. Drop-outs will not be replaced.

7.1.1. Liver Chemistry Stopping Criteria

Liver chemistry stopping, and increased monitoring criteria have been designed to assure participant safety and evaluate liver event etiology.

For all participants, ALT will be done before check-in for each study period. Discontinuation of study treatment for abnormal liver tests is required when the participant shows $ALT \geq 3 \times ULN$.

7.2. Participant Discontinuation/Withdrawal from the Study

- A participant may withdraw from the study at any time at his/her own request or may be withdrawn at any time at the discretion of the investigator for safety, behavioral, compliance or administrative reasons. This is expected to be uncommon.
- If participant is found positive for breath alcohol test in any ambulatory visit, then the ambulatory sample of that particular visit will not be collected. However, he/she may be requested to come for subsequent ambulatory samples in same study period, if continuation in the study is not expected to have any significant impact on the safety or PK outcome in the judgement of Investigator.
- The decision to withdraw the subject if suffering from vomiting/diarrhoea (3 or more consecutive watery stools) at or before two times of median T_{max} (8 hours) will be taken by the Investigator considering the nature and amount of vomitus, likely/anticipated impact on the study outcome and the participants' health status.
- If participant is dropped out due to personal reasons in a given period, he can be continued in subsequent periods if the PK data generated through such participation can be used for statistical analysis.
- At the time of discontinuing from the study, if possible, an early discontinuation visit should be conducted, as shown in the SoA. See SoA for data to be collected at the time of study discontinuation and follow-up and for any further evaluations that need to be completed.
- The participant will be permanently discontinued both from the study treatment and from the study at that time.
- If the participant withdraws consent for disclosure of future information, the sponsor may retain and continue to use any data collected before such a withdrawal of consent.
- If a participant withdraws from the study, he/she may request destruction of any samples taken and not tested, and the investigator must document this in the site study records.

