The whole study will be divided into three periods. For each period, eligible participants will be randomized to either T1T2R, T2RT1 or RT1T2 treatment sequence according to 1:1:1 ratio.

Disclosure Statement: This is an open label study with 3 periods and only the bio-analytical investigator will be blinded to the treatments administered to the subjects.

Number of Participants:

A maximum of 36 participants will be randomly enrolled to study treatment such that approximately 27 evaluable participants complete the study.

Treatment Groups and Duration:

[figure not shown]
Excluding screening period, the duration of clinical phase will be approximately 20 days from Day-1 to Day 19 including a washout period of at least 7 days (not more than 14 days) for each study period.

The participants will be housed from at least 10.50 hrs before dosing until 24.00 hrs post dose in the centre for each study period. Activities beyond 24.00 hrs will be conducted on ambulatory basis.

In each period, single oral dose [Test Product (T1): 1 x 500 mg Tablet or Test Product (T2): 1 x 250 mg Tablet or Reference Product (R): 1 x 500 mg Tablet] of the study treatments will be administered to the participants as per randomization with 240 ± 2 mL of water at ambient temperature under fed condition.

Data Monitoring or Other Committee: No

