8.2. Safety Assessments

Planned time points for all safety assessments are provided in the SoA.

The participants will be monitored for occurrence of adverse events and serious adverse events throughout the study. Safety evaluation will be done on the basis of outcomes of physical examination, vital signs measurement and clinical laboratory results. The activities will be performed during each study period and during post study evaluation as given in the SoA.

Additionally, any other assessment including laboratory test(s) will be done if judged necessary by the Principal Investigator (PI) or authorized trained personnel at any time during the course of study.

Post study evaluation will be done at the time of collection of last PK sample in last study period. Physical examination and measurement of vital signs (blood pressure, pulse rate, respiration rate and body temperature) performed at the time of check-out will be considered for post-study evaluation if the timing of post study evaluation and check-out coincides.

If any participant fails to complete the study or is discontinued from the study, the post-study evaluation will be done either on the day of discontinuation or before/at the end of study. If the post study evaluation is not completed within this time frame due to any reason, the same can be attempted at later stage at the discretion of Principal Investigator.

The reason for not completing the study will be specified in the respective CRF and the clinical report.

The participants may also report spontaneously any inconvenience or AEs to the monitoring staff at any time during the study or after check-out within the total number of days not exceeding the washout period.

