Post study evaluation	:	Upto 10 mL	Upto 10 mL
Discarded heparinised blood (57 x 0.2 mL)	:	11.4 mL	11.4 mL
*For ALT test (before check-in for each	:	6 mL	6 mL

study period)			
Serum β -hCG (3 x 2 mL)	:	-	6 mL
Approximate blood loss	:	367.4 mL	371.4 mL

*Samples for ALT will be collected in PlainTube/ Plain Gel Tube

Blood withdrawal beyond this specified blood volume in the study will be considered as an incidental blood loss.

The incidental blood loss may occur due to following reasons.

1. For performing pending laboratory tests if study participant are primarily screened for other study not having such investigations.
2. For performing pending laboratory tests on the day of check-in for period I if such investigations are not performed on the day of screening due to any reason.
3. For repeating PK sample due to any reason after check-in in the study if required in the opinion of the investigator (example: loss of blood sample due to spillage or breaking of sample container etc).

It is expected that incidental blood loss due to above mentioned reasons will not exceed a blood loss up to 20 ml.

The participants will be compensated as per the compensation policy of CRO.

If additional blood sample is taken for safety evaluation anytime after check in for first period, no compensation will be provided for such blood loss.

Instructions for the collection and handling of biological samples will be specified in the SRM. The actual date and time (24-hour clock time) of each sample will be recorded.

Samples will be used to evaluate the PK of Griseofulvin. Each plasma sample will be divided into 2 aliquots (1 each for PK and a back-up). Samples collected for analyses of Griseofulvin plasma concentration may also be used to evaluate safety aspects related to concerns arising during or after the study.

Name and address details of Bio-Analytical Investigator:

Set# 01 (PK aliquot) will be shipped to:

Name: [name] [REDACTED], Ph.D. (Analytical Chemistry)

Address: Analytical Facility:

Accutest Research Laboratories (I) Pvt. Ltd.,

[name],

Maharashtra, INDIA.

Tel: PPD [REDACTED]

Fax: [REDACTED]

Email : PPD [REDACTED]

Set# 02 (back-up aliquot) will be forwarded to the same analytical laboratory only after confirmation of receipt of Set# 01 by the analytical laboratory, if necessary.

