A validated LC-MS/MS analytical methodology will be used for the determination of Griseofulvin from the human plasma samples. Validation of the methodology will be carried out in accordance with applicable guidelines and the applicable SOP of analytical facility of Accutest Research Laboratories (I) Pvt. Ltd which are designed in accordance with the regulatory guidelines such as USFDA, EMEA, DCGI etc.

The following parameters (as applicable for BE demonstration and for dose proportionality) will be calculated for each participant-formulation combination using the non-compartmental model by using statistical package SAS[®] 9.2 or higher version:

All concentration values below the limit of quantification (BLQ) will be set to zero for the estimation of pharmacokinetic parameters.

If the pre-dose value is >5 percent of C_{max} , the respective period of that subject will be dropped from all PK evaluations and statistical evaluations

The pharmacokinetic samples of subjects dropped out or withdrawn due to vomiting / diarrhoea or any other reason will not be analyzed for the respective study period. The samples of subjects completing at least 2 periods of the study will be subjected to statistical analysis.

Depending upon availability of data, the subject will be either included in bioequivalence evaluation or dose proportionality evaluation.

Primary parameters

C_{max}	Maximum observed drug concentration during the study.
AUC_{0-t}	Area under the plasma concentration - time curve measured to the last quantifiable concentration, using the linear trapezoidal rule.
AUC_{0-inf}	AUC_{0-t} plus additional area extrapolated to infinity, calculated using the formula $AUC_{0-t} + C_t/K_{el}$, where C_t is the last measurable drug concentration and K_{el} is the elimination rate constant.

Secondary parameters

T_{max}	Time to observe maximum drug concentration. If the maximum value occurs at more than 1 time point, T_{max} is defined as the first time point with this value.
AUC_{0-t} / AUC_{0-inf}	Ratio of AUC_{0-t} and AUC_{0-inf}
Residual area	Extrapolated area $(AUC_{0-inf} - AUC_{0-t}) / AUC_{0-inf}$

K_{el}	Apparent first – order terminal elimination rate constant calculated from a semi-log plot of the plasma concentration versus time curve, using the method of least square regression.
$t_{1/2}$	Terminal half-life as determined by quotient $0.693/K_{el}$

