10.5.2. Handling of Missing Data

Element	Reporting Detail
General	
Missing samples can be due to withdrawal of participant and accidental spillage of samples as mentioned in current version of SOP for 'Missing Sample'. Missing sample values (MSV) or non-reportable values (NRV), of the plasma concentration data, will be represented as MSV and NRV in the plasma concentration tables and reasons for their missing will be documented. Any BLQ value occurring between two measurable concentration values will also be treated as missing sample (MS). These missing values will be treated as 'missing values' for Pharmacokinetic and statistical analysis. All the procedures will be performed in accordance with current version of SOP for 'Calculation of Pharmacokinetic Parameters'. For participants with missing or non-reportable concentrations for three or more of the last samples, only the C_{max} and T_{max} will be presented and included in the statistical analysis. Other PK parameters will not be reported. Data from the participants with missing concentrations values (missed blood draws, lost samples, samples unable to be quantified) may be used if pharmacokinetic parameters can be estimated using the remaining data points. Otherwise, concentration data from these participants will be excluded from the final analysis.

Outliers	
 Any participants excluded from the summaries and/or statistical analyses will be documented along with the reason for exclusion in the clinical study report.

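### Loss of a PK period after early vomiting or diarrhoea follows from an unblinded discretionary decision, and its effect on the ratios cannot be tested as planned because the samples are not assayed

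*Protocol*

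**What the plan says.** - **Decision.** Protocol 7.2 covers vomiting, or diarrhoea defined by a stool count, up to 8 h after dosing (twice the median Tmax). Whether the participant is withdrawn "will be taken by the Investigator considering the nature and amount of vomitus, likely/anticipated impact on the study outcome" and the participant's health status.
- **Blinding.** In the Synopsis, "only the bio-analytical investigator will be blinded to the treatments administered to the subjects". Protocol 6.3 opens with "This is an open-label study; potential bias will be reduced by the following steps" and then names computer-generated randomization and blinding of the bioanalytical analyst. Neither step covers the withdrawal decision.
- **Consequence for the data.** Protocol 8.5: "The pharmacokinetic samples of subjects dropped out or withdrawn due to vomiting / diarrhoea or any other reason will not be analyzed" for the period concerned. Protocol 9.3 requires T1 and R for the BE set, and T1 and T2 for the dose-proportionality set. Losing a T1 period therefore removes the participant from both comparisons. Protocol 7.1 does not replace drop-outs.
- **Sensitivity analysis.** Protocol 9.4.4.3 foresees results with and without clinically justified statistical outliers. Neither document does this for periods lost to vomiting or diarrhoea, and the SAP does not mention the rule.
- **Records.** Protocol 8.2: "The reason for not completing the study will be specified in the respective CRF and the clinical report". SAP 10.5.2: "Any participants excluded from the summaries and/or statistical analyses will be documented along with the reason for exclusion in the clinical study report". The adverse event display in SAP 10.2.1 has onset time and last product taken. SAP 10.8.4 lists discontinued subjects, exclusions and adverse events.

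**The concern.** Only the 8 h window and the stool count are objective. Nothing states when an event inside the window costs the period its data, so two similar events may be handled differently. The person deciding knows which product was given and is told to consider the effect on the study. One decision thus settles both a clinical question (does the participant continue?) and a statistical one (does this profile enter the primary analysis?).

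Excluding a period in which the dose was probably not absorbed is not in itself the problem. If it is done by the same rule for every product, it removes a distortion. The harm comes from unequal handling: a reduced profile dropped on one product and a similar one kept on another shifts T1/R or T2/T1 directly. Without assay results, no later analysis can show the size of that shift.

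**Working it through.** **Inputs from Protocol 9.1 and 9.2:** limits 80.00% to 125.00%, 90% confidence interval, assumed ratio 0.95, intra-subject CV 21%, 27 evaluable, 36 randomized.

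**Step 1. Reproduce the plan's sample size.** s_w = sqrt(ln(1 + 0.21²)) = 0.2077 and SE = s_w × sqrt(2/n). Exact power of the two one-sided tests at n = 27 is 90.4% with n − 2 degrees of freedom and 91.1% with 2n − 4. The smallest n for 90% power is 27 or 26 respectively. The stated 27 reproduces.

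**Step 2. Lowest passing estimate at the planned CV**, = 0.80 × exp(t × SE), with 2n − 4 degrees of freedom.
- n = 27: SE = 0.0565, t = 1.676, giving 0.80 × exp(0.0947) = 0.88. Distance from 0.95: 7.4%.
- n = 36: SE = 0.0490, t = 1.668, giving 0.80 × exp(0.0817) = 0.868. Distance from 0.95: 8.6%.

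**Step 3. Shift from keeping rather than dropping k affected profiles on one product.** If an event leaves a fraction f of exposure, the ratio is multiplied by exp(k × ln f / n). The documents give neither f nor k, so both are assumptions, shown as a range.

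| Exposure lost | n | k = 1 | k = 2 | k = 3 |
|---|---|---|---|---|
| 30% | 27 | 1.3% | 2.6% | 3.9% |
| 50% | 27 | 2.5% | 5.0% | 7.4% |
| 70% | 27 | 4.4% | 8.5% | 12.5% |
| 30% | 36 | 1.0% | 2.0% | 2.9% |
| 50% | 36 | 1.9% | 3.8% | 5.6% |
| 70% | 36 | 3.3% | 6.5% | 9.5% |

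For example, at 50% loss and n = 27, exp(−0.6931/27) = 0.975, exp(−1.3863/27) = 0.950 and exp(−2.0794/27) = 0.926.

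**Step 4. Chance of passing.** This was simulated with 36 paired log differences, 20,000 runs, period effects ignored, true ratio 0.95, and events on T1 only. With two participants losing 50% of exposure, the chance of passing is 79% if they are kept and 95% if they are dropped. Across one to four participants losing 30% to 70%, it runs from 94% down to 3% if kept and stays at 94% to 96% if dropped.

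**Step 5. Upper bound on false equivalence.** At a true ratio of 0.80, removing the one, two or three lowest T1/R ratios of 36 raises the pass rate from 5% to about 12%, 19% and 28%. Removing three at random leaves it at about 5%. The bound assumes knowledge of who is lowest, which nobody has before assay.

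**The case against.** A reader might infer that selective exclusion here can be neither prevented nor checked. The documents do not support that. Reasons for non-completion, documented exclusions, the adverse event record by last product taken and the SAP 10.8.4 listings allow early vomiting and diarrhoea events to be tabulated by product, with those kept and those dropped. Protocol 8.5 also keeps a back-up aliquot of every plasma sample, so assay is possible although not planned.

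A reader might also infer that low profiles can be picked out for removal. The non-assay rule implies that the decision comes before that period's concentrations exist. Selection can follow the product and the clinical signs, but not measured exposure. This limit stands, although no deadline for the decision is stated.

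Protocol 7.2 does not make effect on the study the sole criterion: the vomitus and the participant's health also count. The neighbouring bullet on ambulatory visits speaks of safety or PK outcome, so the phrase may well mean whether the dose was absorbed and not whether equivalence is shown. That is a fair reading, but it leaves the judgement unblinded and without a defined threshold.

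The size is also open to challenge. Protocol 7.2 expects withdrawal to be uncommon. The match of 7.4% with 7.4% arises only at n = 27 with three halved profiles, all on one product and all handled differently. With 36 evaluable, three such profiles shift the ratio by 5.6% against a distance of 8.6%.

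Finally, assay may not recover everything. Protocol 7.2 discontinues a withdrawn participant at once. If sampling stops by 8 h, the last six samples (10, 12, 24, 48, 72 and 96 h) are missing, and Protocol 9.4.4.1 then allows only Cmax and Tmax.

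**Conclusion.** The point holds in a limited form. The stated rules permit exclusion from the primary analysis that depends on the product, through a discretionary decision by someone who knows the treatment. Uneven exclusion would be visible in the listings. Its effect on T1/R or T2/T1 would not be testable as planned.

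At 50% exposure loss, the shift is 2.5%, 5.0% or 7.4% for one, two or three unequally handled profiles at n = 27, and 1.9%, 3.8% or 5.6% at n = 36. The distances to the lowest passing estimate are 7.4% and 8.6%. These figures are illustrations that rest on an assumed loss, an assumed number of events, the planned CV and entirely one-sided handling. They show that a few decisions could matter at this sample size, not that bias is expected.

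**What to change.** Leave the participant-withdrawal decision in Protocol 7.2 as the clinical matter it is, and separate inclusion of PK data from it in Protocol 8.5 and 9.3 and in the SAP.

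1. Decide inclusion of an affected period only from recorded facts: the type of event and its time relative to the 8 h window already stated. Use the same rule for T1, T2 and R. Anticipated effect on the study should play no part in the data decision.
2. Have existing study staff without access to the treatment code make and document that decision before assay.
3. Replace the non-assay rule in Protocol 8.5. Assay the samples already drawn unless the participant asks for their destruction, as Protocol 7.2 allows.
4. Report the 90% confidence intervals with and without the affected periods for each parameter that can be estimated. Where sampling stopped early, this may be Cmax only, and the report should say so.

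The cost is wording in both documents, assay of a small number of extra samples and one additional sensitivity table. This is a cheap improvement.
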